1.0 Objectives / Specific Aims

The overall goal of this study is to assess maternal vitamin D status along with diet, and milk composition to, in turn, evaluate if infant vitamin D status can be improved with increased maternal supplementation and diet education. Our **central hypothesis** is that by maximizing maternal vitamin D status, there will be an increase infant 25(OH)D concentration in breastfed, preterm infants. This hypothesis will be tested by performing the following Specific Aims.

Aim 1: Determine the efficacy, effectiveness, and safety of maternal and premature infant vitamin D supplementation as a function of maternal vitamin D status, lactation status, and ethnicity.

H₁: Maternal supplementation of high dose (6,600 IU) vitamin D₃/day will be safe for lactating mothers.

H₂: It is anticipated that only high dose (6,600 IU) vitamin D₃/day supplementation of lactating mothers will provide sufficient antirachitic activity in breast milk to prevent vitamin D deficiency in nursing premature infants, regardless of ethnicity/race.

H₃: High-dose maternal supplementation will be safe and more effective than infant vitamin D supplementation alone, without any adverse side effects or health consequences in the mother or infant.

Consented lactating women who delivered preterm infants <35 weeks' gestation admitted to the MUSC NICU will be randomized 3-7 days following delivery to either 1 of 2 study groups: Group A (standard therapy of 600 IU vitamin D₃/day), Group B (high dose supplementation of 6,600 IU Vitamin D₃/day). As such, infants whose lactating mothers are randomized to the 600-IU/day group will receive 400-IU/day oral vitamin D₃ (recommended practice). Those infants of lactating mothers assigned to Group B will receive placebo. Calcium homeostasis will be monitored in all groups. Safety will be assessed throughout the study on a case-rather than a treatment arm basis using cautionary levels as the stop rule with intervention prior to exceeding normal urinary calcium/creatinine ratios in mothers and serum calcium concentrations in both mothers and infants. Through these proposed studies, the prevalence of vitamin D deficiency among mothers and their infants, and the utility of maternal therapeutic intervention with vitamin D₃ will be assessed.

Aim 2: Aim 2: Evaluate and maximize maternal milk composition.

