3. Daily Vitamin D Supplementation: Infants of mothers who receive 600 IU of vitamin D₃ will receive 400 IU of vitamin D₃ in the form of drops. Infants of mothers who receive 6600 IU of vitamin D₃ will receive placebo drops.

3. General Health Assessment of Infant: At 1 week after delivery and then monthly until 3-months of age, each enrolled infant will undergo a growth (measuring head circumference, weight, length, head circumference, Ponderal index, body mass index [BMI]) and general health assessment.

4. PEAPOD Assessment: Prior to discharge from the NICU, the infant will also be placed in the PEAPOD® for body mass composition analysis. The material and data will be specifically obtained for research purposes. There is minimal risk. This is a safe device in which the infant lays in for 2 minutes.

5. Blood Sample from Infant: At initial visit, 1-, 2- and 3-months of age, each infant will have a blood sample 4mL (<1tsp) taken from either a vein (infant’s hand, arm or foot) or the heel. Total amount obtained will be less than 12mL (<1 1/2 tablespoon). The serum sample will be analyzed for vitamin D and calcium concentration. Parents will be counseled that if their infant is vitamin D deficient, the infant’s primary care physician and they will be contacted regarding the finding(s) with recommended follow-up.

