hypercalciuria and hypercalcemia. There is a small risk that the woman's blood calcium level would increase in response to higher dose vitamin D supplementation. The body responds by excreting calcium in the urine to maintain normal calcium levels. If calcium levels in the blood continue to rise, then serum calcium will increase leading to hypercalcemia. This process takes weeks to months to occur. It takes approximately 3 months to reach steady state on an increased vitamin D intake/regimen. In related studies conducted at MUSC comparing maternal vitamin D supplementation with 400, 2400, or 6400 IU of vitamin D₃/day and their infants for 7 months, there were no differences in infant or maternal safety parameters (22). There were no reported episodes of either hypercalciuria or hypercalcemia in any of the treatment groups. In fact, maternal 25 (OH)D levels were higher in the 6400 IU/day treatment group compared to the 400 IU group. In breastfed infants, there was no statistical difference in the average circulating 25 (OH)D in either treatment arm (22).

- a. To ensure that each lactating mother and her breastfeeding infant and each nonlactating mother (and her formula-feeding infant as a control) maintain normal vitamin D status throughout the study period and not develop hypervitaminosis D, both mother and infant will be screened monthly for hypercalciuria, the first indicator of hypervitaminosis D. All study subjects will be monitored closely for hypervitaminosis D. Operationally, we define caution limits as urinary Ca/creatinine ratio > 0.8 mmol/mmol. Whenever any patient

exceeds the caution limit, a specific case study will be initiated by the Data Safety and Monitoring Committee (DSMC) to examine the contribution of sunlight exposure and other confounding factors. Operationally, we define upper limits as a urinary calcium/creatinine ratio > 1.0 mmol/mmol Ca/creatinine ratio. This is a conservative upper limit as circulating levels achieved in individuals living in sun-rich environments achieve this amount without causing toxicity. The DSMC will be convened to review any patient who exceeds any predefined toxic limit for any outcome. If the elevated levels are unexplained, the patient will be withdrawn from supplementation but will continue to be monitored.

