4. **The Risk of Maternal Vitamin D Supplementation on the Infant:** The developing infant's vitamin D levels are 50% of maternal serum levels at birth and rise gradually over the next 2-3 months if there is adequate delivery or synthesis (by skin). Because mothers who are breastfeeding and who are deficient in vitamin D produce milk that is deficient in vitamin D, there is a need to supplement either the infant directly or the mother herself. This study is designed to increase maternal circulating 25(OH)D levels of lactating women through the use of high dose supplementation. Approximately ~20% of maternal vitamin D passes into the milk, and therefore, the risk of hypervitaminosis D in infants whose mothers are receiving the 6,600 IU/day vitamin D₃ regimen—based on predicted maternal circulating 25(OH)D is extremely low (22). There is a risk of hypovitaminosis D to the infant whose mother is receiving the 600 IU/day D₃ regimen if that infant is not receiving the infant vitamin D₃ drops that are prescribed as part of that treatment arm (Group A).

Minimizing Risk of Hypovitaminosis D Identified by an Infant's Participation in this Study:

As an additional safety measure, if at visit 4, any infant in any treatment arm, circulating 25(OH)D concentration is found to be below normal [defined *a priori* as <20 ng/mL (<50 nmol/L)], will be supplemented with the 400 IU vitamin D/day. If an infant's circulating 25(OH)D concentration is <10 ng/mL (<25 nmol/L) and is associated with a serum calcium level of <7.5 mg/dL (<18.75 nmol/L) at 3 months or older, then compliance of mother with her prescribed vitamin D regimen and that of the infant will be assessed. If mother has been compliant with the prescribed infant vitamin D₃ supplementation and the infant continues to have evidence of vitamin D deficiency with hypocalcemia, the infant will be referred to their pediatrician for further evaluation.

5. **The Risk of Milk Collection:** There is minimal physical risk in donating a milk sample either by using a manual or electric pump.
6. **The Risk of Breach of Confidentiality through Collection of Medical History and Clinical Laboratory Data:** As with any research study, there is a small risk that medical information, laboratory reports and data could become available to individuals outside of the study. All study personnel will adhere to HIPAA guidelines and regulations.

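### The infant deficiency rule in Section 15 item 4 sets a dose only at the last visit, and that dose equals the one Group A infants are already assigned

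*Protocol*

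**What the plan says.** Section 1.0 fixes the infant regimens. In Group A, "infants whose lactating mothers are randomized to the 600-IU/day group will receive 400-IU/day oral vitamin" D₃. For the other arm, "Those infants of lactating mothers assigned to Group B will receive placebo". Section 10.0 repeats both.

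Section 10.0 sets four infant visits, one at about days 3-7 and then at months 1, 2 and 3, with 25(OH)D measured at each: "At initial visit, 1-, 2- and 3-months of age, each infant will have a blood sample".

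The dosing rule is in Section 15 item 4. It opens "As an additional safety measure, if at visit 4, any infant in any treatment arm" and, for a 25(OH)D below 20 ng/mL, states that the infant "will be supplemented with the 400 IU vitamin D/day". A second tier covers 25(OH)D below 10 ng/mL together with low serum calcium. It also applies only from 3 months of age, and it leads to a compliance check and then referral to the pediatrician, not to a dose.

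Two other provisions bear on a low value at an earlier visit. Section 10.0 (infant blood sample) has the parents and the primary care physician contacted, with follow-up recommended. Section 13.0 B has the DSMB notified when a subject's value is outside the reference range.

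On risk, Section 15 item 4 says "There is a risk of hypovitaminosis D to the infant whose mother is receiving the 600 IU/day" regimen, if that infant does not get the drops. It has no matching sentence for Group B infants on placebo.

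**The concern.** The rule has two weaknesses, one of timing and one of content.

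Timing: the infants without direct supplementation are those in Group B. Their study source of vitamin D is their mother's milk, and Section 15 item 3 says of the mother's regimen that "It takes approximately 3 months to reach steady state on an increased vitamin D intake/regimen". The rule acts at the end of that interval, and no later study sample shows whether it worked. A deficient Group B infant at month 1 or 2 then has one of two courses. The contact with the physician may bring no vitamin D, and the infant stays on placebo. Or the physician starts a dose of their own choosing, and the infant is no longer supplied through the mother alone when the primary infant outcome (Section 4.0, 25(OH)D at 3 months) is measured. The protocol controls neither course.

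Content: the rule covers either arm but names a single dose, which half of the design already assigns. An infant who became deficient on 400 IU/day gets no added protection from being told to take 400 IU/day.

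**Working it through.** The protocol gives no figure to reproduce. The check sets the visit schedule and doses side by side.

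**Inputs**
- Infant visits and 25(OH)D samples: days 3-7, months 1, 2, 3 (Section 10.0).
- Trigger: visit 4, 25(OH)D below 20 ng/mL, either arm (Section 15 item 4).
- Dose under the rule: 400 IU/day (Section 15 item 4).
- Direct infant dose by arm: Group A 400 IU/day, Group B 0 IU/day as placebo drops (Sections 1.0 and 10.0).
- Primary infant outcome: 25(OH)D at 3 months (Section 4.0).

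**Step 1: which visit is visit 4.** Visit 1 is days 3-7, visit 2 month 1, visit 3 month 2, visit 4 month 3. The trigger falls at the last of four visits, which is also the primary sample. Samples with no dosing action: 4 - 1 = 3 (initial, month 1, month 2).

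**Step 2: time on placebo before the rule can act.** Taking month 3 as about day 90 (assumption) and the start of drops at days 3-7: 90 - 7 = 83 to 90 - 3 = 87 days, or about 12 weeks.

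**Step 3: change in direct infant dose under the rule, as written, for an adherent infant.**

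| Arm | Before visit 4 | Under the rule | Change |
|---|---|---|---|
| Group A | 400 IU/day | 400 IU/day | 400 - 400 = 0 |
| Group B | 0 IU/day | 400 IU/day | 400 - 0 = +400 |

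If 400 IU was meant as an addition, Group A would total 400 + 400 = 800 IU/day, but the text does not say so.

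**Step 4: what the protocol says elsewhere about dose.** The dosing reference reproduced in Section 3.0 gives 400 units/day for prevention in breastfed infants and 2,000 units daily for 6 weeks to treat infant deficiency: 2,000 / 400 = 5 times the dose in the rule. So the document itself separates a preventive from a treatment dose. Section 2.0 reports earlier studies of 800 and 1,000 IU without significant toxicity.

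**Step 5: earlier cover.** The contact in Section 10.0 and the notice in Section 13.0 can apply after any sample. Neither states a dose or whether the blinded drops continue, and the Section 10.0 contact gives no numerical limit.

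**The case against.** The strongest reply is that a low value before month 3 is not ignored. Parents, physician and DSMB are all to be told, the infants start in the NICU, and Section 15 calls its measure an additional one. This stands. What is missing is narrower: a stated study dose and a decision on the drops.

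A second reply is that the present timing protects the comparison, since no protocol-driven rescue precedes the month-3 sample. That is also right. A reader might infer that the rule biases the primary outcome. It does not, because it is triggered by the visit at which that sample is taken. The matter is one of infant safety, and of uncontrolled dosing by outside physicians.

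Third, visit 4 ends the study and Section 18.0 has leftover product returned, so 400 IU/day for a Group A infant could be read as keeping up a supply that would otherwise stop. That reading is possible. It still leaves a deficient infant on the dose at which deficiency arose, and the text does not say whether the dose replaces or adds to the drops.

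A stronger case is tempting. Section 15 says the infant's "vitamin D levels are 50% of maternal serum levels at birth", and Section 2.0 gives deficiency rates in South Carolina women and a very low vitamin D supply from the milk of deficient mothers. A reader might infer from these that a large share of Group B infants go almost unsupplied. The documents do not support this. The milk figure is for deficient mothers, whereas Group B mothers are assigned 6,600 IU/day, and Section 3.0 expects serum levels to rise within a few weeks. Levels at birth precede any drops, apply to both arms, and do not measure what the visit-4 timing causes. Nor is all of Group A affected: the zero change applies only to those who are both adherent and below 20 ng/mL at visit 4.

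**Conclusion.** The point holds in a limited form. Two facts rest on the text alone: three of the four infant 25(OH)D results carry no study dose, and the rule adds 0 IU/day for an adherent Group A infant found deficient. The span of about 12 weeks on placebo assumes that month 3 is near day 90. The number of infants affected, in either arm, is unknown and cannot be estimated from the protocol.

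Group B infants are not untreated by design, since their mothers take 6,600 IU/day. Whether that is enough for preterm infants is the trial's own hypothesis, and Section 2.0 knows of no study on it. That is a reason to have a defined action during follow-up. The Group A dose is the clearer fault, because correcting it after the primary sample costs the comparison nothing. The month 1-2 step is also a gain in safety, but its threshold is partly a trade-off with the maternal-only contrast.

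**What to change.** Amend Section 15 item 4 in three places.

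1. **Visit 4, after the primary sample.** For 25(OH)D below 20 ng/mL, an infant who took placebo starts 400 IU/day, and an infant already on 400 IU/day goes to 800 IU/day, unless the treating physician chooses another dose. Investigational Drug Services supplies the dose by allocation. This has no effect on the primary comparison, and 800 IU/day is a dose that Section 2.0 reports as without significant toxicity.

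2. **Months 1 and 2, as a safety step.** An infant in either arm below 10 ng/mL, the severe limit already used in item 4, receives open-label 400 IU/day on top of the blinded drops. Totals are 0 + 400 = 400 IU/day in Group B and 400 + 400 = 800 IU/day in Group A. The start date and dose are recorded, the arm is not disclosed, and the month-3 sample is still taken.

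3. **Risk paragraph.** Name hypovitaminosis D as a risk for Group B infants, who receive placebo drops.

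The cost is a few sentences and some extra drops. No visit or sample is added, because the month 1 and 2 samples are already planned. The real price lies in step 2: Group B infants who receive it lose the maternal-only contrast at month 3, in a number the documents do not allow to be estimated. A limit of 20 ng/mL would treat more infants and cost more contrast. The 10 ng/mL limit leaves infants between 10 and 20 ng/mL on their assigned drops, with the existing contact and notice, until visit 4.

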There are several studies evaluating various supplementation regimens in preterm infants; however, considerable attention has not been given to the role of maternal vitamin D supplementation and its effects on preterm neonate's vitamin D status. Many groups have recommendations on vitamin D supplementation that have failed to form a consensus or have differing recommendations for preterm neonates. The AAP Committee on nutrition recommends 200-400 IU of vitamin D for very low birthweight infants (VLBW). On the other hand, the European Society of Pediatric Gastroenterology and Nutrition (ESPGAN) recommends 800-1600 IU daily (13). Due to the lack of substantial data, these various groups fail to make recommendations on arguably those at highest risk--preterm, very low birthweight (VLBW) infants, and extremely low birthweight (ELBW) infants. Along with variations in supplementation recommendations, there are also variations among scientific groups as to an ideal target 25(OH)D level. The AAP recommends 25(OH)D > 20 ng/mL (50 nmol/L) (14) and in the same year another group published a paper with recommended 25(OH)D > 30 ng/mL (75 nmol/L) (15). The Endocrine Society targets >30 ng/mL (75 nmol/L) (16) while ESPGAN >32 ng/mL (80 nmol/L) (13). Previous groups have looked at the effects of various vitamin D supplementation regimens in preterm infants, many of which have not shown significant changes in infant 25(OH)D concentrations, but have shown that higher supplementation leads to improved length, head circumference, and possibly immune function (17). Previous studies have shown safety of increased vitamin D supplementation with 800 IU and 1000 IU without significant toxicity (18-20).

In a previous randomized control trial performed at this institution by [name] and colleagues, maternal supplementation with 6400 IU/day of vitamin D₃ was more effective in achieving

vitamin D sufficiency in mothers without increased risk to infants or mothers (21, 22). This present pilot study plans to replicate this in mothers and their preterm infants (22). See IRB application attachments for this paper that is *in press*.

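### The infant serum calcium trigger prints two values that do not match: 7.5 mg/dL is about 1.87 mmol/L, not 18.75 nmol/L

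*Protocol*

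**What the plan says.** In the protocol, Section 15 (Risks to Subjects), item 4, the part on minimizing the risk of hypovitaminosis D gives two infant rules.

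- An infant in either arm with 25(OH)D below 20 ng/mL (50 nmol/L) at visit 4 is to receive 400 IU of vitamin D per day.
- A second rule covers severe deficiency with low calcium. It applies when two conditions hold together: "circulating 25(OH)D concentration is <10 ng/mL (<25 nmol/L") and "associated with a serum calcium level of <7.5 mg/dL (<18.75 nmol/L) at 3 months or older".

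When the second rule is met, "then compliance of mother with her prescribed vitamin D regimen and that of the infant will be assessed". If the regimen was followed and deficiency with hypocalcemia persists, "the infant will be referred to their pediatrician for further evaluation".

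Section 4.0 lists infant serum calcium as a safety endpoint at the initial visit and at months 1, 2 and 3. Section 15, item 3, gives numeric limits for calcium in urine only: "we define caution limits as urinary Ca/creatinine ratio > 0.8 mmol/mmol", with an upper limit of 1.0 mmol/mmol. The 7.5 mg/dL figure in item 4 is therefore the only numeric serum calcium limit in the protocol.

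**The concern.** A bracketed SI value beside a conventional-unit limit should be the same limit in other units. Here it is not. The bracket also carries the unit and the apparent scaling of the 25(OH)D condition earlier in the sentence, which suggests that the vitamin D conversion was applied to calcium.

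The line is a decision threshold in a safety rule for preterm infants. Suppose the bracketed value were carried into a database flag or applied to a laboratory report in SI units. Read as nmol/L, the calcium condition could never be met. Read as mmol/L, every infant would meet it, and the rule would reduce to the 25(OH)D condition alone.

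**Working it through.** **Inputs**

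- Infant calcium limit, conventional units: 7.5 mg/dL (Section 15, item 4).
- Infant calcium limit, bracketed: 18.75 nmol/L (same sentence).
- 25(OH)D pairs in the protocol: 10 ng/mL with 25 nmol/L and 20 ng/mL with 50 nmol/L (Section 15, item 4); 30 ng/mL with 75 nmol/L (Section 2.0, "The Endocrine Society targets >30 ng/mL (75 nmol/L")).
- Molar mass of calcium: 40.078 g/mol. This is a physical constant and is not in the protocol.

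**Step 1: can the printed 18.75 be reproduced?**

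The 25(OH)D pairs all share one factor: 25/10 = 50/20 = 75/30 = 2.5.

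Applied to the calcium limit: 7.5 x 2.5 = 18.75.

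This gives the printed number, but 2.5 converts ng/mL of 25(OH)D to nmol/L and is not valid for calcium. No valid calcium conversion gives 18.75:

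| Conversion of 7.5 mg/dL | Result |
|---|---|
| mmol/L, exact molar mass | 1.871 |
| mmol/L, rounded factor 0.25 | 1.875 |
| mEq/L (two charges per ion) | 3.74 |
| nmol/L | 1,871,351 |

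**Step 2: the correct equivalent**

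mmol/L = (mg/dL x 10) / 40.078 = 75 / 40.078 = 1.871 mmol/L.

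**Step 3: what the bracket means as printed (nmol/L)**

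18.75 x 10⁻⁹ mol/L x 40.078 g/mol = 7.51 x 10⁻⁷ g/L = 7.5 x 10⁻⁵ mg/dL, or 0.000075 mg/dL.

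Ratio to the stated limit: 1,871,351 / 18.75 = 99,805, so the bracket is about 100,000 times too low.

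**Step 4: is it only a misread unit (nmol for mmol)?**

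18.75 mmol/L x 40.078 / 10 = 75.1 mg/dL.

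75.1 / 7.5 = 10.0, so the bracket would then be ten times too high. Correcting the unit alone does not reconcile the two values, and neither does correcting the number alone.

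**The case against.** The arithmetic is not in dispute. The case on the other side is about weight, and much of it stands.

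- **The error is unlikely to mislead.** The mg/dL value is printed first, the trial runs at one US institution, and the bracket is physiologically impossible under either reading. The rule also names hypocalcemia, so its direction is clear. This stands.
- **Other provisions cover much of the same ground.** Any infant below 20 ng/mL at visit 4 receives 400 IU/day whatever the calcium level (Section 15, item 4). Parents and the infant's physician are told of vitamin D deficiency (Section 10.0, Infant, blood sample item). Bottles are checked for compliance at each of the three follow-up visits (Section 18.0). This largely stands, although the notification in Section 10.0 is tied to vitamin D deficiency and does not mention low calcium.
- **The rule has a narrow window.** It applies from 3 months of age and the last study visit is at month 3, so within the schedule it can act at one visit. This stands.
- **The origin of the error is inferred.** A decimal slip together with n for m would turn 1.875 mmol/L into the same printed text. That is fair. The carried-over factor of 2.5 is a likely cause, not a proven one, and the finding does not depend on it.
- **The urinary limits do not settle the serum unit.** A calcium/creatinine ratio in mmol/mmol is not a serum concentration. This is also fair. That ratio shows only that Section 15 works in mmol for calcium elsewhere.

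None of this makes the bracket correct, and nothing elsewhere in the protocol corrects it.

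**Conclusion.** The bracketed value is wrong as written, in both number and unit. The equivalent of 7.5 mg/dL is 1.87 mmol/L (1.875 with the rounded factor), and only the mg/dL value in the rule can be used.

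The point is minor. The limit acts only together with 25(OH)D below 10 ng/mL. It leads to a compliance assessment and possibly a referral, not to a dose change or a stop. The primary endpoints, sample size and analysis are untouched.

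The conclusion rests on the molar mass of calcium and on taking 7.5 mg/dL as the intended limit. The protocol contains nothing that would support the bracketed value instead.

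**What to change.** Confirm with the sponsor that 7.5 mg/dL is the intended limit, then print the calcium condition in Section 15, item 4, as <7.5 mg/dL (<1.87 mmol/L). If the bracketed figure has been copied into any data-entry check or laboratory alert, correct it there too.

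In the protocol, the cost is one number and one unit. Design, visit schedule, sample size and analysis do not change.
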